Therefore, with this study we plan to: (I) compare the end tidal CO2 levels observed during upper endoscopy in children managed with endotracheal intubation or laryngeal mask airway using CO2 versus air and compare how these levels deviate from the pre-procedure baseline levels. (ii) Observe whether there are particular pre-procedural risk factors that predispose children to hypercapnia with CO2 use during upper endoscopy. (iii) Determine if carbon dioxide gas use for insufflation results in significant changes in the minute ventilation. This is a Double-blinded, prospective, randomized study of all pediatric patients undergoing procedures involving upper endoscopy in the Childrens Hospital & Medical Center. Children from 6 months to 19 years of age undergoing upper endoscopy related procedures. Randomization will for intubated patients who require an advanced airway (endotracheal intubation or laryngeal mask airway) 1:1 for air or CO2. Risks assessed before the procedure will include past medical history, American Society of Anesthesiology (ASA) classification. Vital signs will be recorded before the procedure, throughout the procedure and after the procedure until fully awake. While in the procedure room, end-tidal CO2 level and minute ventilation (tidal volume X RR) will be continuously recorded. Patients and legal guardians who decline participation in the study and patients with chronic respiratory disease (defined as severe asthma, bronchopulmonary dysplasia and CF related pulmonary disease), cyanotic heart disease and ASA status ≥ 3 will be excluded from the study.

PURPOSE OF THE STUDY AND BACKGROUND

2. Purpose of the Study

What are the specific scientific objectives of the research?

- (I) Compare the end tidal CO₂ levels observed during upper endoscopy in children managed with endotracheal intubation or laryngeal mask airway using CO₂ versus air and compare how these levels deviate from the pre-procedure baseline levels.
- (ii) Observe whether there are particular pre-procedural risk factors that predispose children to hypercapnia with CO₂ use during upper endoscopy.
- (iii) Determine if carbon dioxide gas use for insufflation results in significant changes in the minute ventilation

3. Background and Rationale

Describe the background of the study. Include a critical evaluation of existing knowledge, and specifically identify the information gaps that the project is intended to fill.

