Luminal inflation is crucial for proper visualization and advancement of the endoscope during endoscopy (2). Air has been the standard insufflation gas during endoscopy. However, multiple adult studies have demonstrated decreased abdominal discomfort and increased efficacy with carbon dioxide (CO₂) use (3-9). Therefore, many adult endoscopy centers now use carbon dioxide routinely for endoscopy insufflation. Only 3 pediatric studies exist on the use of CO₂ for colonoscopy (10-12). Two of these studies demonstrated that CO₂ use was associated with decreased abdominal discomfort after colonoscopy. During my fellowship, we showed, through a recent survey of fellow trainees across North America, that though air remains the predominant gas for insufflation during endoscopy in pediatrics, CO₂ is increasingly being used. We have also demonstrated through our study that CO₂ use during upper endoscopy in children is associated with significant elevations in end-tidal CO₂ levels. This finding is likely the result of eructated CO₂ used during upper endoscopy, as most of the patients in our study did not have the airway isolated by intubation. It is also possible that there is excessive direct absorption of CO₂ from the upper GI tract. This study has been written up and the manuscript is awaiting editorial decision. It has been presented at a national conference (Digestive Disease Week, San Diego; May 2019). In a follow up study, CO₂ use during upper endoscopy was not associated with significant elevations in transcutaneous CO₂ level.

We hypothesize that transient elevations in end tidal CO₂ level observed with CO₂ use during upper endoscopy is due to eructation of the instilled gas and will be eliminated by protection of the airway. We also hypothesize that there will be no changes in minute ventilation associated with CO₂ use during upper endoscopy in patients who are intubated (via endotracheal tube or laryngeal mask airway).

**Amendment- We will now enroll 19 year old's (Adults) into this study and also Spanish Speaking subjects.

CHARACTERISTICS OF THE SUBJECT POPULATION

4. Accrual

A. Is this study conducted solely at sites under the oversight of the UNMC IRB (e.g. UNMC, Nebraska Medicine, CHMC, UNO)?

Yes

1. How many subjects will need to be consented (per group, as applicable) in order to achieve the scientific objectives of the research?

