After it has been determined that the patient can be included in the study and the consents have been signed; the procedure nurse will open the first envelope and randomly pick either CO₂ or Air. She will then set up the insufflation gas based on the gas picked. She will cover the air and CO₂ dispensing machine so that the patient, anesthesiologist and endoscopist are all blinded to the type of insufflation gas used during the procedure. She will complete randomization using the cards in each set of envelope before moving to the next set. The endoscopy room/procedure room nurse will keep a record of patients randomized into the air or CO₂ group in a locked cabinet. She will assign arbitrary letters or numbers to the gas used so that the biostatistician who will perform the interim analysis will be blinded to the arm of

study as well.

- Data including age, gender, weight z scores, BMI, co-morbid factors and reason for endoscopy will be collected on all children enrolled in the study. Name and level of expertise of the endoscopist will be collected including the duration of both the procedure and anesthesia and any procedural or anesthesia related complications encountered during the procedure or within forty-eight hours of the procedure.
- Vital signs including heart rate, respiratory rate, blood pressure, end tidal CO₂ level and minute ventilation (tidal volume x respiratory rate) will be recorded before the procedure and continuously monitored during the procedure as per anesthesia protocol.
- Information regarding end tidal CO₂ level and minute ventilation will be recorded for both groups and compared to the pre-procedure values. We will also collect data on the type of anesthetic medications used and the presence of any of these symptoms (nausea, vomiting or headaches) after the procedure. Please also see attached flow chart below for protocol and randomization.

C. Select any of the following that apply to the research:

Phase I study

♦ Randomization

Placebo (or non-treatment arm)

Washout

Sensitive surveys or questionnaires

None of the above

Describe randomization process and schedule

This is a double blinded , randomized clinical study. Both the endoscopist and patients will be blinded to the insufflation gas used; Air or CO₂. The procedure room/ endoscopy room nurse will then randomize the patients as described below:

The nurse will receive 4 envelopes.

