Continuous data will be reported as means with standard deviations, or medians with interquartile ranges depending if variable has normal or skewed distribution respectively. Categorical variables will be described by percentages and proportions. Comparisons of continuous data will be performed using the t-test or Wilcoxon signed-ranks test. Categorical variables will be compared using the chisq test or Fishers exact test. A probability value <.05 will be considered significant. Statistical analysis will be performed using SAS 9 statistical software (SAS Institute, Cary, NC) or Graph Pad Prism 7 for Windows (Graph pad Software, San Diego, CA).

Descriptive statistics, including counts and %, means, SD, medians, will be used to summarize patient characteristics, procedural, anesthesia and safety outcomes for the two groups. Patient characteristics, Patient safety outcomes;(MV, EtCO₂), procedural, and anesthesia outcomes will be compared between the groups using the independent sample t-test or Mann-Whitney test or Fishers exact test as appropriate to the data. Changes in these safety outcome measurements across the monitoring period between the two groups using a mixed effects model will be considered

F. Does this study involve the collection of blood, urine, saliva or other human biological material (HBM)?

No

DRUGS, BIOLOGIC DRUGS AND DEVICES

13. Drugs and Biologic Drugs

1. Does this research involve the use of drugs or biologics?

No

14. Devices

1. Does this research involve a medical device(s)?

No

CONFIDENTIALITY AND PRIVACY

15. Confidentiality and Privacy

A. Describe where research data will be stored. Check all that apply.

♦ On a secure server at UNMC, CHMC, Nebraska Medicine, and/or UNO (including REDCap)

On a secure cloud server - Specify the secured cloud serve:

On a firewall protected database accessible through the internet - Specify who has administrative responsibility for maintenance of the server:

On an encrypted, password protected local hard drive

On an encrypted, password protected portable computer

On an encrypted, password protected flash drive

♦ In hard copy

♦ Other Hard copies of the original signed consent and assent forms will be stored in a locked file cabinet, or in a lock briefcase when not in use

a. Please provide justification for use of hard copies

Hard copies of consent and assent are required and are kept as per institutional policy.

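### No committed between-arm analysis uses the recorded pre-procedure EtCO₂ and minute ventilation, and minute ventilation has no size scaling from 6 months to 19 years

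*Combined protocol and SAP*

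**What the plan says.** - **Objectives (Section II, item 2).** Objective (i) compares EtCO₂ under CO₂ and air and is also to "compare how these levels deviate from the pre-procedure baseline levels". Objective (iii) is to "Determine if carbon dioxide gas use for insufflation results in significant changes in the minute ventilation".
- **Hypothesis (item 3).** "We also hypothesize that there will be no changes in minute ventilation associated with CO₂ use during upper endoscopy in patients who are intubated".
- **Data (item 12.B).** "end tidal CO₂ level and minute ventilation (tidal volume x respiratory rate) will be recorded before the procedure and continuously monitored during the procedure". Also: "end tidal CO₂ level and minute ventilation will be recorded for both groups and compared to the pre-procedure values". No between-arm method is attached to that comparison. On body size: "Data including age, gender, weight z scores, BMI, co-morbid factors and reason for endoscopy will be collected on all children enrolled".
- **Analysis (item 12.E).** The committed between-arm comparison is "Patient characteristics, Patient safety outcomes;(MV, EtCO₂), procedural, and anesthesia outcomes will be compared between the groups using the independent sample t-test or Mann-Whitney test". Categorical outcomes go to Fisher's exact test. On change over time: "Changes in these safety outcome measurements across the monitoring period between the two groups using a mixed effects model will be considered". An earlier sentence of 12.E also offers a Wilcoxon signed-rank test for continuous data without saying which comparison it serves.
- **Sample size (item 4).** The calculation is a two-sided two-sample t-test on mean EtCO₂ over the monitoring period, with 75 per group, a 2 mmHg difference and SD 4.3 mmHg. It has no baseline term.
- **Population (item 9).** Ages run from 6 months to 19 years.

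**The concern.** The trial collects the baseline values its objectives call for, but no analysis it commits to uses them to compare the arms. The one model that addresses change is optional and has no stated baseline term.

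MV is where this matters most. As defined, it is an absolute volume per minute, and an infant and a 19-year-old differ in it largely because they differ in size. No per-kilogram, log or percent-of-baseline scale is stated. A weight z score is already standardised, so it cannot by itself scale MV. Size-driven spread goes into the error term of an unadjusted test and can hide a moderate difference between arms. Because the protocol hypothesises no change in MV, a non-significant result from a noisy test could be read as support.

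For EtCO₂ less is at stake. Randomisation makes the unadjusted comparison valid, but the interval is wider than it need be and chance baseline imbalance stays in the estimate.

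**Working it through.** **Inputs from the documents (item 4).** 75 per arm after dropout, difference 2 mmHg, SD 4.3 mmHg, two-sided alpha 0.05.

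**Assumed, because the documents do not give them.** The correlation r between the baseline and procedure values; the coefficient of variation (CV) of MV; and equal SDs before and during the procedure.

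**Step 1: the plan's own figure.** The exact two-sample t-test (noncentral t) needs 74 per arm for 80% power and gives 80.8% at 75. Dropout: 75 / (1 − 0.25) = 100. The stated sample size reproduces.

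**Step 2: EtCO₂ with baseline.**

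- ANCOVA residual SD = 4.3 × √(1 − r²)
- Change-score SD = 4.3 × √(2(1 − r))
- 95% CI half-width = t × SD × √(2/75). Unadjusted, this is 1.976 × 4.3 × 0.1633 = 1.39 mmHg.

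| r | ANCOVA SD | ANCOVA power | CI half-width (mmHg) | Change-score power |
|---|---|---|---|---|
| unadjusted | 4.30 | 80.8% | 1.39 | – |
| 0.2 | 4.21 | 82.3% | 1.36 | 60.9% |
| 0.3 | 4.10 | 84.3% | 1.32 | 66.7% |
| 0.5 | 3.72 | 90.4% | 1.20 | 80.8% |
| 0.7 | 3.07 | 97.7% | 0.99 | 95.5% |

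Below r = 0.5 a simple change score does worse than ignoring baseline; ANCOVA does not. If baseline SD is also 4.3, the standard error of the baseline difference between arms is 4.3 × √(2/75) = 0.70. Chance alone can then put the arms up to about 1.96 × 0.70 = 1.4 mmHg apart at baseline (95% range), against a target of 2 mmHg.

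**Step 3: MV, 75 per arm.**

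- Unadjusted detectable difference as a share of the mean = 2.82 × CV × √(2/75). At CV 40% this is 2.82 × 0.40 × 0.1633 = 18.4%.
- Log SD = √(ln(1 + CV²)), which is 0.385 at CV 40% and 0.472 at CV 50%.
- Residual log SD = log SD × √(1 − r²), with r on the log scale.
- Detectable ratio = exp(2.82 × residual log SD × √(2/75)). At CV 40% and r = 0.8 the residual is 0.385 × 0.6 = 0.231 and the ratio is 1.112.

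| Analysis | Detectable difference, CV 40% / 50% | Power for a 10% difference, CV 40% / 50% |
|---|---|---|
| Unadjusted, absolute MV | 18.4% / 23.0% | 33% / 23% |
| Log ANCOVA, r = 0.2 | 19.0% / 23.8% | 34% / 24% |
| Log ANCOVA, r = 0.3 | 18.4% / 23.1% | 35% / 25% |
| Log ANCOVA, r = 0.5 | 16.6% / 20.7% | 41% / 29% |
| Log ANCOVA, r = 0.8 | 11.2% / 13.9% | 71% / 53% |
| Log ANCOVA, r = 0.9 | 8.0% / 9.9% | 93% / 80% |

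The gain comes from the baseline, not from the log scale. If the CV were only 20%, the unadjusted test would already have 86% power for a 10% difference.

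**The case against.** The best defence is that 12.E answers a form question asking for a brief description. It does not rule out scaling MV or testing change from baseline. Read with objective (i) and 12.B, an independent t-test of change scores could be what was meant. That reading is hard to sustain: 12.E assigns MV and EtCO₂ to the t-test and leaves their changes to the optional mixed model, and the sample size uses the EtCO₂ level. It is fair, though, that the lack of MV scaling is inferred from the definition and from silence.

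Other parts of the defence stand:

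- The EtCO₂ t-test is valid, matches the sample-size test and meets its stated power. Adjusting it is an improvement, not the correction of an error.
- The MV figures depend on an assumed CV and r. Near r = 0.3 the gain vanishes, and large gains need r around 0.8 to 0.9. Body size affects both readings, which makes a high r plausible, but the documents do not establish it.
- All figures use 75 per arm. With no dropout and 100 per arm, unadjusted EtCO₂ power is 90.5% and the detectable MV difference at CV 40% is 15.9%.
- The list of collected data is not exhaustive, so actual weight may be available.
- The between-group sentence in 12.E already names Mann-Whitney, which leaves the signed-rank test for within-patient comparisons. That point is only a clarification.

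**Conclusion.** The concern holds. The plan commits to no between-arm analysis that uses the recorded baseline, although objectives (i) and (iii) are framed around baseline and change, and it states no size scaling for MV across a very wide age range.

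Randomisation means there is no bias on average, and the sample size is not wrong. The cost is precision. For EtCO₂, power at 75 per arm would rise from 80.8% to between 82% and 98% for r from 0.2 to 0.7. For MV, at an assumed CV of 40 to 50%, the detectable difference would fall from 18–23% to 11–14% at r = 0.8, with essentially no gain at r = 0.3 or below. The MV figures are illustrative.

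This should be changed because the method is better and the baseline data are already being collected. Baseline adjustment would not by itself support a conclusion that MV is unchanged; that is a separate question.

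**What to change.** Revise 12.E to commit to the following:

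1. **EtCO₂, primary between-arm analysis:** ANCOVA of each patient's mean EtCO₂ on arm and pre-procedure EtCO₂, reported as a mean difference with 95% CI. Do not use a simple change score.
2. **MV:** ANCOVA of log mean MV on arm and log pre-procedure MV, reported as a ratio with 95% CI. Each child's own baseline then serves as the control for size, without needing actual weight.
3. **Mixed model:** if it is to be used, commit to it and give it the same baseline covariate.
4. **Clarification:** signed-rank for within-patient comparisons only, Mann-Whitney for between-arm comparisons.
5. **Baseline:** define which reading counts. Where recorded, use the one taken after airway placement and before insufflation.

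Items 1 to 4 need wording only, because both baselines are already recorded. Item 5 may need an added data field, since 12.B says only that readings precede the procedure. Airway type (endotracheal tube or laryngeal mask) is an optional covariate; 12.B does not list it among the data collected, so it too may need a field.

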230 subjects total (100 each group). This extra 30 subjects will allow for screen failures that occur on the study for example change in plans from use of ETT or LMA to nasal cannula in the procedure room after subjects may have been consented. They will not be randomized and need to be replaced on the study.

2. What is the statistical or other justification for the total number of subjects described above?

Sample sizes of 75 per group achieve 80% power to detect a difference of 2 mmHg between the null hypothesis that both group mean EtCO₂ measurement over the length of the monitoring period are 37.2 mmHg and the alternative hypothesis that the mean of the CO₂ group is 39.2 with an estimated within group standard deviation of 4.3 mmHg and with a significance level (alpha) of 0.05 using a two-sided two-sample t-test. To adjust for the possibility of a 25% drop out rate 100 patients per group will be enrolled.

We have also allowed 30 extra subjects due to some screen failures we have had.

5. Gender of the Subjects

A. Are there any enrollment restrictions based on gender?

No

6. Age Range of Subjects

A. Will adults be enrolled ?

Yes

1. What is the age range of the adult subjects?

The adults in this study will be 19 years old.

2. What is the rationale for selecting this age range?

As we were enrolling subjects into this study we noticed we had several 19 year old subjects still being seen by our GI Department. Therefore, they would qualify for the study. We did

not want to exclude them from participating in the study. The research will be conducted in children aged 6 months to 19 years to determine if end tidal CO₂ remains persistently elevated in intubated children undergoing upper endoscopy with CO₂ insufflation and to determine if there are changes in minute ventilation with CO₂ use during upper endoscopy.

B. Will children (18 years of age or younger) be included in this research?

Yes

1. What is the justification for inclusion of children in this research?

The research will be conducted in children aged 6 months to 18 years to determine if end tidal CO₂ remains persistently elevated in intubated children undergoing upper endoscopy with CO₂ insufflation and to determine if there are changes in minute ventilation with CO₂ use during upper endoscopy.

2. What is the age range for the child subjects, and what is the justification for selecting this age range?

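### EtCO₂ and minute ventilation are compared one at a time, so a flat EtCO₂ alone cannot separate no absorption from absorption offset by ventilation

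*Combined protocol and SAP*

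**What the plan says.** The abstract (Section II, item 1) gives the motive: to learn whether the EtCO₂ elevations seen earlier in non-intubated children were absorbed gas or only eructated gas. Section 3 hypothesises that the rise "is due to eructation of the instilled gas and will be eliminated by protection of the airway" and, as a separate hypothesis, that MV will not change. MV is also objective (iii) in Section 2.

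Section 12.B records EtCO₂ and MV before the procedure. Both are then "continuously monitored during the procedure as per anesthesia protocol" and compared with the pre-procedure values. The anesthesiologist is blinded to the gas; nothing says that the EtCO₂ reading is hidden. The data items listed there do not include ventilation mode or changes of ventilator setting.

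For analysis, Section 12.E states that "Patient characteristics, Patient safety outcomes;(MV, EtCO₂), procedural, and anesthesia outcomes will be compared between the groups" by t-test, Mann-Whitney or Fisher's test. A mixed model for changes over the monitoring period is only to be considered. No joint or MV-adjusted analysis is named. No weight scaling or baseline adjustment is stated for the between-group MV test, although Section 9 admits ages 6 months to 19 years.

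Section 4 sizes the trial on mean EtCO₂ only: "Sample sizes of 75 per group achieve 80% power to detect a difference of 2 mmHg", with an "estimated within group standard deviation of 4.3 mmHg". No SD, margin or power is given for MV.

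**The concern.** Absorbed CO₂ leaves through the lungs. For a given load, more ventilation means a lower EtCO₂. A flat EtCO₂ in the CO₂ arm therefore fits two accounts: nothing was absorbed, or gas was absorbed and cleared by extra ventilation. Blinding to the gas prevents deliberate unequal care by arm, but it does not prevent a response to the EtCO₂ reading, and a child breathing spontaneously may raise MV unaided. On fixed settings MV cannot respond, so an unchanged MV there says nothing about objective (iii). Without ventilation mode in the data, these cases cannot be told apart afterwards.

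At stake is the answer to the trial's own question. If a real load is split between a small EtCO₂ rise and a small MV rise, both separate tests can be non-significant, and the pair may then be taken to support both Section 3 hypotheses.

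**Working it through.** **Inputs from Section 4.** Null: "both group mean EtCO₂ measurement over the length of the monitoring period are 37.2 mmHg". Alternative: "the alternative hypothesis that the mean of the CO₂ group is 39.2". SD 4.3 mmHg, 75 per group, "significance level (alpha) of 0.05 using a two-sided two-sample t-test".

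**Plan's own figure.** n = 2 × (1.960 + 0.842)² × 4.3² / 2² = 72.6, so 73 per group; the exact t calculation gives 74. At 75 per group the standard error is 4.3 × √(2/75) = 0.702 and the noncentrality 2/0.702 = 2.85, giving 81% power. With 25% dropout, 75/0.75 = 100. The sample size reproduces.

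**Assumed model (not in the documents).** EtCO₂ is proportional to CO₂ load / MV, with constant dead space and steady state. The design difference is then a load increase L = 39.2/37.2 − 1 = 5.4%. If a share s of it is met by ventilation, MV rises by sL and the EtCO₂ difference is 37.2 × [(1 + L)/(1 + sL) − 1].

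| Offset s | MV rise | EtCO₂ difference (mmHg) | EtCO₂ power, 75 per arm |
|---|---|---|---|
| 0 | 0% | 2.00 | 81% |
| 25% | 1.3% | 1.48 | 55% |
| 50% | 2.7% | 0.97 | 28% |
| 75% | 4.0% | 0.48 | 10% |
| 100% | 5.4% | 0 | 5% (alpha) |

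**Does the MV test catch what EtCO₂ loses?** The standardised MV effect is the MV rise divided by its coefficient of variation (CV). The documents give no CV, so 10% to 50% is assumed. At full offset MV power is 91%, 59%, 37%, 19% and 10% for CVs of 10%, 15%, 20%, 30% and 50%. Treating the tests as independent, the chance that both are non-significant is:
- half offset: (1 − 0.28) × (1 − MV power), with MV power 37% at CV 10% and 6% at CV 50%, giving 45% to 67%;
- full offset: 0.95 × (1 − MV power), giving 9% to 86%.

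**A joint index.** Take the within-patient change in log(EtCO₂ × MV). Under the model it shows the whole load, ln(1.054) = 0.052, whatever the offset. With an assumed SD of 0.15 to 0.25 on this change:
- standard error = SD × √(2/75) = 0.0245 to 0.0408;
- noncentrality = 2.14 to 1.28;
- power = about 57% to 25%;
- 95% CI half-width = 1.976 × SE = 0.048 to 0.081.

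An observed difference of exactly zero would just exclude a 5.4% excess at SD 0.15, and would not at SD 0.25. For a 10% load (ln 1.10 = 0.095) index power is 97% to 64%.

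**Index against the two planned tests.** Give MV the same log SDs (0.15 to 0.25). At half offset of the 5.4% load, MV power is 19% to 10%, so at least one planned test is significant with probability 1 − 0.72 × 0.81 = 42% to 1 − 0.72 × 0.90 = 35%, unadjusted for multiplicity. The index has 57% to 25%. It wins at the lower SD and loses at the higher.

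**The case against.** The strongest reply is that MV is already the plan's check on compensation. It is an objective, has its own hypothesis, and is compared with pre-procedure values. A large rise in MV with flat EtCO₂ would be visible and would contradict the second hypothesis. The two extremes also partly protect the trial: on fixed settings EtCO₂ carries the whole load and keeps its 81% power, and with full offset MV carries it. This stands. What remains is the partial offset, the unquantified MV test across a very wide age range, and the lack of any statement on how the two results are read together.

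Four stronger readings are tempting, and the documents do not support them:
- That a flat EtCO₂ will be taken as proof of eructation. Section 3 states a hypothesis, not a decision rule.
- That absence of elevation clears CO₂ for use. Section 20 runs one way only: persistent elevation may lead to limits.
- That ventilation will be adjusted in response to EtCO₂. No section says so. The flow chart and the anesthesia protocol mentioned in Section 12.B were not available to check.
- That a joint index restores power. It does not do so reliably, as the last comparison shows. Inferring no absorption from a non-significant index would miss a real 5.4% load about 43% to 75% of the time, which repeats the mistake of treating non-significance as absence.

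**Conclusion.** The point holds as one of interpretation and analysis choice, not as an arithmetic error; the sample size is right for its own inputs. Separate tests of EtCO₂ and MV leave the absorbed-or-eructated question open when EtCO₂ is flat and MV is imprecise. At the 5.4% load, EtCO₂ power falls from 81% with no offset to 28% at half offset and 5% at full offset. These figures rest on the assumed EtCO₂–load/MV relation and on offset shares that the documents do not give; the MV and index figures rest further on assumed variability, and the both-tests figures on independence. A reader might infer that the plan ignores MV; it does not, and a large offset would show there. The gap is the missing joint reading, with no stated baseline adjustment or weight scaling for the between-group MV test and no ventilation mode in the listed data.

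**What to change.** In Section 12.E:
1. Keep the EtCO₂ comparison as planned.
2. Analyse MV as the within-patient log change from the pre-insufflation value, which removes the constant effect of body size.
3. Add, as a supportive pre-specified analysis, the between-arm difference in within-patient change in log(EtCO₂ × MV), with its 95% CI.
4. State that absorption will be ruled out only if EtCO₂ and MV are read together and the CI for the joint index excludes a pre-specified margin, never because a test is non-significant. The investigators should choose and justify the margin before unblinding.

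In Section 12.B, add ventilation mode and setting changes, taken from the anesthesia record, to the listed data, and report MV results by mode.

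The cost is a few sentences, two fields and one analysis of data already recorded. The downside is that MV adds noise and the index may be inconclusive, so it should sit beside EtCO₂. No change to ventilation practice is proposed.
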